9.2.1.1. Adverse Events of Special Interest

The following AEs of special interest will be used to determine the safety and tolerability of ixekizumab injections in this clinical study.

Adverse events of special interest for ixekizumab are:

- cytopenias (leukopenia, neutropenia, and thrombocytopenia)
- liver function test changes/enzyme elevations (ALT, AST, TBL, and ALP)
- infection

- ISRs
- allergic reactions/hypersensitivities
- cerebrocardiovascular events
- malignancies
- depression
- inflammatory bowel disease (Crohn's disease and ulcerative colitis)
- interstitial lung disease

If infections, ISRs, or allergic/hypersensitivity reactions are reported, sites will provide details on these events as instructed on the eCRF. Investigators will also educate subjects about the symptoms of allergic/hypersensitivity reactions and will provide instructions on dealing with those reactions. A blood sample will be collected when possible for any subject who experiences an AE of allergic/hypersensitivity reaction during the study.

Data on cerebrocardiovascular events (defined as death, myocardial infarction, stroke, hospitalization for unstable angina, hospitalization for heart failure, coronary revascularization procedure, peripheral revascularization procedure, cardiogenic shock due to myocardial infarction, resuscitated sudden death, serious arrhythmia, hospitalization for hypertension, and peripheral arterial event) will be collected and the events will be adjudicated by an external Clinical Events Committee (CEC) made up of a chair, 2 cardiologists, and a neurologist.

Data on suspected inflammatory bowel disease, as identified by events possibly indicative of ulcerative colitis and Crohn's disease, will be collected. Suspected IBD cases will be adjudicated by an external CEC composed of gastroenterologists with expertise in inflammatory bowel disease

The role of the CEC is to adjudicate defined clinical events, in a blinded, consistent, and unbiased manner throughout the course of the study. The importance of the CECs is to ensure that all events that have been reported are evaluated uniformly by a single group.

9.2.1.2. Suspected Unexpected Serious Adverse Reactions

Suspected unexpected serious adverse reactions (SUSARs) are serious events that are not listed in the IB and that the investigator reports as related to IP or procedure. Lilly has procedures that will be followed for the recording and expedited reporting of SUSARs that are consistent with global regulations and the associated detailed guidances.

9.2.2. Complaint Handling

Lilly collects product complaints on IPs and drug delivery systems used in clinical trials in order to ensure the safety of study participants, monitor quality, and to facilitate process and product improvements.

Subjects should be instructed to contact the investigator as soon as possible if he or she has a complaint or problem with the IP or drug delivery system so that the situation can be assessed.

The investigator or his/her designee is responsible for handling the following aspects of the product complaint process in accordance with the instructions provided for this study:

- Recording a complete description of the product complaint reported and any associated AEs using the study-specific complaint forms provided for this purpose
- Faxing the completed Product Complaint Form within 24 hours to Lilly or its designee.

If the investigator is asked to return the product for investigation, he/she will return a copy of the Product Complaint Form with the product.

9.3. Treatment of Overdose

For the purposes of this study, an overdose of ixekizumab is considered any dose higher than the dose assigned through randomization. Syringes used in this study can deliver only 1 mL volume of ixekizumab

There is no specific antidote for ixekizumab. In the event of an overdose, the subject should receive appropriate supportive care and any AEs should be documented.

Refer to the Taltz Product Label.

9.4. Safety

Safety will be assessed throughout the course of the study at site visits and via telephone calls in between site visits.

9.4.1. Laboratory Tests

For each subject, laboratory tests detailed in Appendix 2 should be conducted according to the Schedule of Activities (Section 2).

9.4.2. Vital Signs

For each subject, vital signs measurements should be conducted according to the Schedule of Activities (Section 2).

Blood pressure and pulse rate should be measured after at least 5 minutes sitting. Additional vital signs may be assessed as clinically indicated as well as at the scheduled times.

Unscheduled orthostatic vital signs should be assessed, if possible, during any AE of dizziness or posture-induced symptoms. Additional vital signs may be measured during each study period if warranted.

9.4.3. Electrocardiograms

For each subject, ECGs should be collected according to the Schedule of Activities (Section 2).

Any clinically significant findings from unscheduled ECGs that result in a diagnosis and that occur after the subject receives the first dose of the IP, should be reported to Lilly, or its designee, as an AE via eCRF.

Electrocardiograms must be recorded before collecting any blood samples. Subjects must be supine for approximately 5 to 10 minutes before ECG collection and remain supine but awake during ECG collection. Electrocardiograms may be obtained at additional times, when deemed clinically necessary. All ECGs recorded should be stored at the investigational site.

Electrocardiograms will be interpreted by a qualified physician (the investigator or qualified designee) at the site as soon after the time of ECG collection as possible, and ideally while the subject is still present, to determine whether the subject meets entry criteria at the relevant visit(s) and for immediate subject management, should any clinically relevant findings be identified.

If a clinically significant finding is identified after enrollment, the investigator will determine if the subject can continue in the study. The investigator, or qualified designee, is responsible for determining if any change in subject management is needed, and must document his/her review of the ECG printed at the time of collection. Any new clinically relevant finding should be reported as an AE.

9.4.4. Temperature

Body temperature will be assessed at the times indicated in the Schedule of Activities (Section 2).

9.4.5. Other Tests

9.4.5.1. Injection-Site Assessments

Injection-site assessments will be performed at the times indicated in the Schedule of Activities (Section 2).

If the investigator determines that any ISR is clinically significant or if a subject indicates symptoms are indicative of an ISR (unsolicited event; volunteered by subject), the event will be captured as an AE.

Induration, swelling, pruritus, and erythema/redness associated with study injection sites will be evaluated by the blinded assessor.

9.4.5.2. Bleeding/Bruising Assessment

All injection sites will be observed at the times indicated in the Schedule of Activities (Section 2) by the blinded assessor, and the presence of visible bleeding/bruising will be recorded on the eCRF. A bandage may be placed on the injection site after assessment.

9.4.5.3. Injection-Site Pain

Pain measurements will be quantified using the 100-mm VAS pain score for all subjects. The VAS is a well-validated tool (Williamson and Hoggart 2005) to assess injection-site pain; it is presented as a 100-mm line anchored by verbal descriptors, usually "no pain" and "worst imaginable pain." The subject will be asked to relate any pain at the injection site on a scale of 1 to 100 mm on the line immediately (within 1 minute) following injection and at the time points listed in the Schedule of Activities (Section 2).

9.4.5.4. Columbia Suicide Severity Rating Scale

Columbia Suicide Severity Rating Scale: a scale that captures the occurrence, severity, and frequency of suicidal ideation and/or behavior during the assessment period. The scale includes suggested questions to solicit the type of information needed to determine if suicidal ideation and/or behavior occurred. Any occurrence of suicide-related thoughts and behaviors will be assessed as indicated in the Schedule of Activities (Section 2) using the C-SSRS. The C-SSRS is administered by an appropriately trained healthcare professional with at least 1 year of patient care/clinical experience.

The nonleading AE collection should occur prior to the collection of the C-SSRS. If a suicide-related event is discovered during the C-SSRS but was not captured during the nonleading AE collection, sites should not change the AE form. If an event is serious or leads to discontinuation, this is an exception where the SAE and/or AE leading to discontinuation should be included on the AE form and the process for reporting SAEs should be followed. The first time the scale is administered in this study, the C-SSRS 'Baseline – Screening' version will be used, and the findings will constitute the baseline assessment. The C-SSRS 'Since Last Visit' scale will be used for all subsequent assessments. The Lilly Self-Harm Supplement should be completed every time the C-SSRS is administered. If there are positive findings on the Self-Harm Supplement, then the Lilly Self-Harm Follow-up form will be used to collect additional information to allow for a more complete assessment of these behaviors.

9.4.5.5. Hospital Anxiety Depression Scale

The HADS depression subscale is a 7-item self-assessment scale that determines the levels of depression that a subject is experiencing over the past week. The HADS depression subscale utilizes a 4-point Likert scale (e.g., 0 to 3) for each question and is intended for ages 12 to 65 years (Zigmond and Snaith 1983; White et al. 1999). The score can range from 0 to 21, with higher scores indicating greater depression (Zigmond and Snaith 1983; Snaith 2003).

9.4.6. Safety Monitoring

The Lilly CP or CRP/scientist will monitor safety data throughout the course of the study.

Lilly will review SAEs within time frames mandated by company procedures. The Lilly CP or CRP will periodically review trends in safety data, laboratory analytes, and AEs.

When appropriate, the Lilly CP or CRP will consult with the functionally independent Global Patient Safety therapeutic area physician or clinical research scientist.

9.4.6.1. Hepatic Safety

If a study subject experiences elevated ALT \geq 3 × ULN, ALP \geq 2 × ULN, or elevated TBL \geq 2 × ULN, liver tests (Appendix 4) should be repeated within 3 to 5 days including ALT, AST, ALP, TBL, conjugated bilirubin, gamma-glutamyl transferase, and creatinine phosphokinase to confirm the abnormality and to determine if it is increasing or decreasing. If the abnormality persists or worsens, clinical and laboratory monitoring should be initiated by the investigator based on consultation with the Lilly CP or CRP. Monitoring should continue until levels normalize and/or are returning to approximate baseline levels.

Additional safety data should be collected if 1 or more of the following conditions occur:

- elevation of serum ALT to $\geq 5 \times ULN$ on 2 or more consecutive blood tests
- elevated serum TBL to $\ge 2 \times \text{ULN}$ (except for cases of known Gilbert's syndrome)
- elevation of serum ALP to $\ge 2 \times ULN$ on 2 or more consecutive blood tests
- subject discontinued from treatment due to a hepatic event or abnormality of liver tests
- hepatic event considered to be an SAE

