This will be a single-dose, subject-blind, 3-period, 3-treatment, randomized, crossover study in healthy subjects. Eligible subjects will be admitted to the clinical research unit (CRU) on Day -1 and randomized 1:1:1 to 1 of 3 possible treatment sequences.

Subjects may be allowed to leave the CRU after completing the 4-hour safety assessments for Day 1, at the investigator's discretion. Subjects will be readmitted to the CRU on Days 7 and 14 to receive their second and third injections on Days 8 and 15, respectively, and may be allowed to leave the CRU after completing the 4-hour safety assessments at the investigators discretion on Days 8 and 15, respectively. Subjects will return to the CRU as an outpatient on Days 21 (± 1 day) and 43 (± 3 days) for a safety check-up. In addition, safety follow-up telephone calls will be conducted in between outpatient visits, on Days 28 (± 1 day), 35 (± 3 days), 50 (± 3 days), 57 (± 3 days), and 64 (± 3 days), with a final safety follow-up telephone call on Day 71 (± 3 days). There will be a follow-up visit approximately 12 weeks after the last injection.

Safety and tolerability will be assessed by monitoring of adverse events (AEs), injection-site assessments, injection-site pain, bleeding/bruising assessments, Columbia Suicide Severity Rating Scale (C-SSRS), Hospital Anxiety Depression Scale (HADS), vital signs assessments, temperature, physical examination, 12-lead electrocardiograms (ECGs), and clinical laboratory tests. Pain assessments will be made using an injection-site visual analog scale (VAS).

Treatment Arms and Planned Duration for an Individual Subject:

All subjects will be screened within 28 days prior to enrollment. On Days 1, 8, and 15, subjects will receive a single 1-mL subcutaneous injection of 1 of the following treatments, according to the randomization schedule:

• 80 mg ixekizumab Commercial Formulation (Reference)

- 80 mg ixekizumab Test Formulation 1
- 80 mg ixekizumab Test Formulation 2

Subjects will participate in the study for approximately 18 weeks.

Number of Subjects:

Up to 102 subjects may be enrolled to maximize the intent to have 78 subjects (26 in each treatment sequence) complete the study. Attempts will be made to enroll a total of 3 Japanese completers.

Statistical Analysis:

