Physical Exam		X											X	After baseline exam, medical assessment is performed only to include medical review and targeted examination, as appropriate.
12-lead ECG	X												X	Single readings will be taken after at least 5 minutes in a supine position.

	Screening		Study Day											Comments
Procedure	-28 to -2 days prior to Day 1	Day -1	Day 1	Day 7	Day 8	Day 14	Day 15	Day 21 (± 1 day)	Days 28 & 35 (± 3 days)	Day 43 (± 3 days)	Days 50, 57, & 64 (± 3 days)	Day 71 (± 3 days)		
HADS Depression sub-scale	X	X		X		X		X		X			X	
C-SSRS and Lilly Self-Harm Supplement	Х	X		X		X		X		X			X	At screening 'Baseline - Screening' questionnaire to be used, all other timepoints use 'Since Last Visit' questionnaire.
Body Temperature			P	X		X		X		X			X	
Clinical Chemistry, Hematology, and Urinalysis Tests	Х	X		X		X		X		X			X	See Appendix 2, Clinical Laboratory Tests, for details.

	Screening	Study Day										FU/ ED ^a	Comments	
Procedure	-28 to -2 days prior to Day 1	Day -1	Day 1	Day 7	Day 8	Day 14	Day 15	Day 21 (± 1 day)	Days 28 & 35 (± 3 days)	Day 43 (± 3 days)	Days 50, 57, & 64 (± 3 days)	Day 71 (± 3 days)		
Injection-Site Assessments (Minutes)			0, 10, 20, 30, 60, 120, 240		0, 10, 20, 30, 60, 120, 240		0, 10, 20, 30, 60, 120, 240	X		X				Assessments of induration, swelling, pruritus, and erythema/redness (collected as described in Section 9.4.5.1). 0-minute time point should be done within 1 minute following injection; within ± 2 minutes of the 10, 20, and 30-minute time points; within ± 5 minutes of the 60, 120, and 240-minute time points. Assessments will be conducted once during the 1-week follow-up on Day 21 (± 1 day) and on Day 43 (± 3 days).
Injection-Site Pain Assessment using VAS (Minutes)			0, 10, 20, 30, 60		0, 10, 20, 30, 60		0, 10, 20, 30, 60							Assessment of injection-site pain (VAS) at the 0-minute time point should be done within 1 minute following injection; within \pm 2 minutes of the 10, 20, and 30-minute time points; within \pm 5 minutes of the 60-minute time point.
	Screening	5		Study Day									FU/ ED ^a	Comments

Procedure	-28 to -2 days prior to Day 1	Day -1	Day 1	Day 7	Day 8	Day 14	Day 15	Day 21 (± 1 day)	Days 28 & 35 (± 3 days)	Day 43 (± 3 days)	Days 50, 57, & 64 (±3 days)	Day 71 (± 3 days)		

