8.1. Discontinuation from Study Treatment

Discontinuation of the IP for abnormal liver tests **should be considered** by the investigator when a subject meets 1 of the following conditions after consultation with the Lilly designated medical monitor:

- alanine aminotransferase (ALT) or aspartate aminotransferase (AST) >5 × upper limit of normal (ULN)
- ALT or AST >3 × ULN sustained for more than 2 weeks
- ALT or AST >3 × ULN and total bilirubin level (TBL) >2 × ULN or International Normalized Ratio >1.5
- ALT or AST >3 × ULN with the appearance of fatigue, nausea, vomiting, right upper quadrant pain or tenderness, fever, rash, and/or eosinophilia (>5%)
- alkaline phosphatase (ALP) >3 × ULN;
- ALP $> 2.5 \times ULN$ and TBL $> 2 \times ULN$;
- ALP > 2.5 × ULN with the appearance of fatigue, nausea, vomiting, right quadrant pain or tenderness, fever, rash, and/or eosinophilia (>5%)

In addition, subjects will be discontinued from the study drug in the following circumstances:

- Neutrophil (segmented) counts:
 - o <500 cells/μL
 - \circ \geq 500 and <1000 cells/ μ L (based on 2 test results; the second test performed within 1 week from knowledge of the initial result)
 - $\circ \geq 1000$ and < 1500 cells/ μL (based on 3 test results) and an infection that is not fully resolved
- Total white blood cell count <2000 cells/µL
- Lymphocyte count <200 cells/μL
- Platelet count <50,000 cells/μL

Subjects will also be evaluated for discontinuation from study treatment if a suicide-related thought or behavior is identified at any time during the study, or if during the study a subject gives:

- a "yes" answer to Question 4 (Active Suicidal Ideation with Some Intent to Act, Without Specific Plan) on the "Suicidal Ideation" portion of the C-SSRS
- a "yes" answer to Question 5 (Active Suicidal Ideation with Specific Plan and Intent) on the "Suicidal Ideation" portion of the C-SSRS
- a "yes" answer to any of the suicide-related behaviors (actual attempt, interrupted attempt, aborted attempt, preparatory act, or behavior) on the "Suicidal Behavior" portion of the C-SSRS

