9.2. Adverse Events

Investigators are responsible for monitoring the safety of subjects who have entered this study and for alerting Lilly or its designee to any event that seems unusual, even if this event may be considered an unanticipated benefit to the subject.

The investigator is responsible for the appropriate medical care of subjects during the study.

Investigators must document their review of each laboratory safety report.

The investigator remains responsible for following, through an appropriate health care option, AEs that are serious or otherwise medically important, considered related to the IP or the study, or that caused the subject to discontinue the IP before completing the study. The subject should be followed until the event resolves, stabilizes with appropriate diagnostic evaluation, or is reasonably explained. The frequency of follow-up evaluations of the AE is left to the discretion of the investigator.

After the informed consent form is signed, study site personnel will record, via eCRF, the occurrence and nature of each subject's preexisting conditions. Additionally, site personnel will record any change in the condition(s) and the occurrence and nature of any AEs.

The investigator will interpret and document whether or not an AE has a reasonable possibility of being related to study treatment or a study procedure, taking into account concomitant treatment or pathologies.

A "reasonable possibility" means that there is a potential cause and effect relationship between the IP and/or study procedure and the AE.

Planned surgeries should not be reported as AEs unless the underlying medical condition has worsened during the course of the study.

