# 9.3.6 Hepatic Monitoring

If a subject experiences elevated alanine aminotransferase (ALT)  $\ge 3 \times$  upper limit of normal (ULN), alkaline phosphatase (ALP)  $\ge 2 \times$  ULN, or elevated total bilirubin (TBL)  $\ge 2 \times$  ULN, liver tests will be performed to confirm the abnormality. Additional safety data may be collected if required, as defined in the protocol. Where applicable, the following will be presented.

The subjects' liver disease history and associated person liver disease history data will be listed. Any concomitant medication of acetaminophen/paracetamol will be listed. Results from any hepatic monitoring procedures, such as a magnetic resonance elastography (MRE) scan, and a biopsy assessment will be listed, if performed.

Hepatic risk factor assessment data will be listed. Liver related signs and symptoms data will be summarized by formulation and listed. Alcohol and recreational drug use data will also be listed.

All hepatic chemistry, hematology, coagulation, and serology data will be listed. Values outside the reference ranges will be flagged on the individual subject data listings.

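### Low-priority improvement: an isolated AST rise does not trigger the 3-to-5-day liver retest that an equal ALT rise does

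*Protocol*

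**What the plan says.** **Retest rule.** Protocol 9.4.6.1 sets three triggers: ALT ≥3 × ULN, ALP ≥2 × ULN and TBL ≥2 × ULN. When one is met, "liver tests (Appendix 4) should be repeated within 3 to 5 days including ALT, AST, ALP, TBL, conjugated bilirubin, gamma-glutamyl transferase, and creatinine phosphokinase". The purpose is to confirm the finding and see which way it is moving. The next step depends on the result: "If the abnormality persists or worsens, clinical and laboratory monitoring should be initiated by the investigator", in consultation with the sponsor physician.

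**Second tier.** The same section lists conditions for collecting additional safety data. Its aminotransferase condition is ALT ≥5 × ULN on at least two consecutive tests. AST is not named.

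**SAP.** The trigger sentence in SAP 9.3.6 begins "If a subject experiences elevated alanine aminotransferase (ALT" and goes on to ALP and TBL at the same thresholds. It says that confirmatory tests will be done but gives no time window.

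**Where AST counts.** Protocol 8.1 has seven liver criteria for considering discontinuation of study drug. The first four apply to either aminotransferase; the third, for example, reads "ALT or AST >3 × ULN and total bilirubin level (TBL) >2 × ULN or International Normalized Ratio >1.5". Section 9.2.1.1 lists, among events of special interest, "liver function test changes/enzyme elevations (ALT, AST, TBL, and ALP". Appendix 2 includes AST in the routine chemistry panel.

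**Schedule.** After the first dose, the row "Clinical Chemistry, Hematology, and Urinalysis Tests" in the Schedule of Activities is marked at Days 7, 14, 21 and 43 and at follow-up. On the last of these, 5.1 states: "There will be a follow-up visit approximately 12 weeks after the last injection".

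**The concern.** AST is used to decide whether study drug should be stopped, is singled out for special attention, and is remeasured once another analyte has triggered a repeat. Yet an AST rise on its own does not start a repeat. The uncovered case is AST ≥3 × ULN with ALT below 3 ×, ALP below 2 × and TBL below 2 × ULN.

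At stake is safety follow-up. Without a prompt second value it is not known whether the rise is real, or whether it is going up or down, and the monitoring step in 9.4.6.1 has nothing to start from. Two of the three formulations had not been given to humans or animals before (Protocol 3.1), so timely confirmation has some value.

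**Working it through.** The plan gives no figure to reproduce. The check compares the rules and then counts days to the next required AST measurement.

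**Step 1: AST across the liver rules**

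| Rule | Does AST alone count? |
|---|---|
| Protocol 8.1, liver criteria | Yes, in 4 of 7 |
| Protocol 9.2.1.1, special interest | Yes |
| Protocol 9.4.6.1, repeat panel | Measured, once another analyte has triggered |
| Protocol 9.4.6.1, repeat triggers | No, 0 of 3 |
| Protocol 9.4.6.1, enzyme-level conditions for additional data | No |
| SAP 9.3.6, triggers | No, 0 of 3 |

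**Step 2: days to the next required AST**

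Inputs from the Schedule of Activities: chemistry on Days 7, 14, 21 (±1) and 43 (±3). Follow-up is about 12 weeks after the last injection (Day 15), ±1 week: 15 + 84 = Day 99, range 99 − 7 = 92 to 99 + 7 = 106. Gap = next sampling day minus day of the rise. Excess = nominal gap minus 5, to nominal gap minus 3.

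| Rise first seen | Nominal gap (days) | With windows | Excess over an ALT rise |
|---|---|---|---|
| Day 7 | 14 − 7 = 7 | no window stated | 7 − 5 = 2 to 7 − 3 = 4 |
| Day 14 | 21 − 14 = 7 | 20 − 14 = 6 to 22 − 14 = 8 | 2 to 4 |
| Day 21 | 43 − 21 = 22 | 40 − 22 = 18 to 46 − 20 = 26 | 22 − 5 = 17 to 22 − 3 = 19 |
| Day 43 | 99 − 43 = 56 | 92 − 46 = 46 to 106 − 40 = 66 | 56 − 5 = 51 to 56 − 3 = 53 |
| Follow-up | no later scheduled sample | – | – |

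**Step 3: could the gap change a dosing decision?**

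Injections are on Days 1, 8 and 15. Scheduled samples on Days 7 and 14 already give an AST value the day before the second and third. A 3-to-5-day repeat of a Day 7 rise would fall on Days 10 to 12, and Day 14 supplies another value before the last dose anyway. A repeat of a Day 14 rise would fall on Days 17 to 19, after the last dose. The two-week persistence criterion in 8.1 cannot be met before Day 15 by a rise first seen on Day 7, because 15 − 7 = 8 days. The effect on dosing is therefore close to nil, and the long gaps begin only after dosing has ended.

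**Step 4: do other rules set an interval?**

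The remaining routes by which AST could enter the additional-data list in 9.4.6.1 are discontinuation of treatment for a liver abnormality and a hepatic SAE. After Day 15 no treatment is left to discontinue, so only the SAE route remains. The telephone calls on Days 28, 35, 50, 57, 64 and 71 fall inside the two long gaps but draw no blood.

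**The case against.** **A coherent ALT scheme.** Both tiers of 9.4.6.1 use ALT, ALP and TBL, which looks more like a deliberate choice than a dropped word. AST is also less specific to the liver. This has force: 8.1 governs stopping drug and 9.4.6.1 governs retesting, so different triggers are not a contradiction. A reader might infer a drafting error, but the documents show only an asymmetry with no stated reason.

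**Existing safeguards.** Section 9.2 states: "Investigators must document their review of each laboratory safety report". It also requires serious, medically important or treatment-related adverse events to be followed to resolution, stabilisation or explanation. The sponsor physician reviews laboratory trends (9.4.6), safety calls fall between visits, and Appendix 5 allows extra safety samples. A reader might infer that an isolated AST rise would go unnoticed; the documents do not support that. What stands is narrower: none of these provisions fixes when AST must be measured again.

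**Little relevance to 8.1.** The long gaps start after the last injection, when 8.1 has nothing left to stop. This is correct, and it limits the benefit to follow-up.

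**INR.** Because one 8.1 criterion uses INR, a reader might infer that the repeat omits a test it needs. The documents do not establish this: 9.4.6.1 refers to Appendix 4, which contains prothrombin time and INR, and its list of named tests is open.

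**The SAP.** A reader might also infer that SAP 9.3.6 carries the 3-to-5-day window. It shares only the triggers, so changing the SAP alone would not alter when anyone is retested.

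**Conclusion.** The point holds as a cheap, low-priority improvement to safety follow-up. Its size is a delay in the required recheck of an isolated AST rise: 22 days from Day 21 and about 56 days from Day 43, against 3 to 5 days for an equal ALT rise. On nominal days that is 17 to 19 and 51 to 53 days longer. At Days 7 and 14 the excess is 2 to 4 days.

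These figures assume that ALT, ALP and TBL stay below their triggers and that nobody orders a discretionary sample. The documents give no rate of isolated AST elevation, so the number of subjects affected is unknown and may be zero. Appendix 6 records that enrolment of new subjects had stopped by amendment (b), so only subjects still in follow-up could benefit. The primary VAS endpoint, its model and the sample size are not touched.

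**What to change.** - In Protocol 9.4.6.1, change the first trigger to *ALT or AST ≥3 × ULN*.
- In the same section, change the first additional-data condition to *ALT or AST ≥5 × ULN* on at least two consecutive tests, so that the asymmetry does not survive in the second tier.
- In SAP 9.3.6, match the trigger list to the protocol.

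The cost is two phrases in a further protocol amendment, one phrase in the SAP, and one extra draw for each subject with an isolated AST rise. AST is already in the routine panel. Some of these rises will not be hepatic; creatinine phosphokinase, already a named repeat test, helps to tell them apart.
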